## 6 Potential Risks and Benefits

### 6.1 Risks

(a) Subjective discomfort. In pilot testing, participants may experience discomfort speaking to an RA and discussing experiences they choose to share regarding their child's and their own unmet needs and treatment. All participants will be reminded that they can decline to answer any questions if they so choose.

(b) Breach of confidentiality. As with any research setting, a breach of confidentiality is possible. Participants' identifying information will not be included in the analytic dataset or publication, therefore the risk to participants' confidentiality is minimized.

(c) Intervention burden. Subjects may feel that the intervention or research measures are time consuming or that scheduling is burdensome. Every effort will be made to diminish burden for subjects. Burden of the intervention is part of what we will be testing in this pilot study.

## 6.2 Potential Benefits

The goal of the study is to diminish the impact that unmet social needs create for families with preschool aged children with ADHD. Participants may directly benefit by receiving this new intervention, which has been developed based on both quantitative and qualitative formative work, and is an adapted version of WE CARE, an existing, evidence-based social needs intervention. Participants in the intervention arm will have the opportunity to be connected with resources using a strategy that has been specifically tailored to the needs of families with preschoolers who have inattention and/or hyperactivity symptoms. Participants in both arms will have access to their clinic's usual care pathway. In some cases, for participants on waiting lists for specialty care, they would receive this intervention as well as the clinical measures while they are waiting, when they would otherwise not receive any support or care from the clinic. Additionally, participants in both arms will complete standardized psychiatric questionnaires (the CBCL for ages 1.5-5 and ADHD-RS-IV Preschool Version) that could help clinical care and can be shared with providers via the EMR with permission of parents. Additionally, the information collected from this study will be used to refine the intervention, which we are testing as a method of improving ADHD symptoms in preschoolers. By being in the study, participants are helping investigators learn if this intervention could improve ADHD in preschoolers.

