### 3.2 Rationale and Purpose

The goal of this proposed study is to pilot test a novel treatment model (PRE-CARE) addressing unmet social needs for families of preschool-age children with ADHD symptoms. We will conduct an adaptive, pilot randomized controlled trial (RCT) of the intervention with parents of 60 low-income children age 3-5 (36-71 months) with ADHD symptoms in order to: optimize intervention delivery; field test study logistics (e.g., recruitment, enrollment, randomization, retention); explore putative intervention mechanisms; and obtain estimates of study parameters to plan an appropriately powered RCT of the intervention. The PRE-CARE intervention is adapted from WE CARE, a screening and referral intervention that has been shown to be feasible and effective in addressing the family psychosocial stressors of low-income families seen in pediatric medical homes. Given the negative impact that socioeconomic stressors can have on the health and development of young children with ADHD symptoms, tailored interventions such as PRE-CARE may serve as a vital early intervention strategy to promote long-term well-being.

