### 4.2 Study Outcome Measures

#### 4.2.1 Primary Outcome Measures

**Primary outcomes** include the following clinical outcomes:

- ADHD Symptoms (ADHD-RS-IV Preschool Version)
- Child Psychiatric Symptoms (Child Behavior Checklist 1.5-5)

**Secondary outcomes** include the following measures of unmet social needs, treatment access and utilization, parent activation, parent mental health/stress, adverse childhood experiences, and feasibility/acceptability:

- Unmet Social Needs Outcomes (Children's Health Watch Vital Signs and National Survey of Children's Health pertaining to all unmet needs in the PRECARE Screener).
- Adverse Childhood Experiences (CYW ACE-Q)
- Parental Depression (PHQ-9)
- Parental ADHD (ASRS-v1.1)
- Global Perceived Stress (PSS)
- Parenting Stress (PSI-SF)
- PRE-CARE Feasibility and Acceptability Questionnaire
- Semi-structured in-depth exit interviews with parent/guardians on feasibility/acceptability

**Process outcomes** include the following measures of study and intervention processes:

- **Recruitment and enrollment statistics** (number of parent/guardians referred and from which clinic, contacted, screened, eligible, refused participation, enrolled, dropped out of study or intervention early and why, and completed intervention)
- **Contacts with parent/guardians** (number, frequency, modality, length)
- **Referrals made** (including agencies, date of referral, and parent/guardian vs. staff referral)
- **Resources accessed** (including specific resource accessed, resource category, date accessed)
- **Needs resolved** (date at which a participant indicates they no longer need help with a need and why)

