## 7 Study Subject Selection

### 7.1 Subject Inclusion Criteria

In order to be eligible to participate in this study, an individual must meet all of the following criteria:

1. Legal guardian and primary caregiver of a child aged 36-71 months
2. Legal guardian or primary caregiver is age 16 years or older
3. Child receives pediatric care at Boston Medical Center or at one of the participating Boston HealthNet clinics
4. Able to understand informed consent procedures in English or Spanish
5. Participant has a child aged 36-71 months with an ADHD diagnosis, OR one elevated total or subscale score at the 80th percentile on the ADHD-Rating Scale-IV Preschool Version. 80th percentile cut-offs on the ADHD-Rating Scale-IV Preschool Version are as follows:
  - For male children, a total score  $\geq 25$  OR subscale score (inattention and/or hyperactivity)  $\geq 12$
  - For female children, a total score  $\geq 13$  OR subscale score (inattention and/or hyperactivity)  $\geq 6$  for female children

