Participants completing the electronic REDCap form will provide an e-signature typing in their name and date, or drawing their signature on the screen (phone, computer, or tablet/iPad) with their finger, mouse, surface pen, etc. Parent or legal guardian consent will be required to participate in the study. Study staff members are trained in Boston University Medical Campus (BUMC) IRB policy and will closely follow consent procedures as outlined by the BUMC IRB. Potential subjects will be provided the consent document which details the background, purpose and procedures of the study. The study details will be reviewed with potential participants who will be given the opportunity to ask questions about the study and their participation. All participants will be given, mailed or emailed an unsigned copy of the consent form for their records. They may additionally be given, mailed or emailed a copy of their signed consent form, if requested.

If a participant indicates that they are interested in participating in the study, but cannot schedule a study visit to complete the informed consent procedures, or have previously missed their scheduled study visit, participants will have a period of 3 months to decide their participation and schedule a study visit. After the 3-month period, interested participants will be required to be re-screened as eligibility criteria may have changed. Research study staff will then re-administer the screening procedure to determine study eligibility.

As this study will enroll Spanish-speaking participants, the consent form will be translated into Spanish by the BMC interpreter services. The consenting process and interviews will be conducted in Spanish by fluent Spanish speakers or with the assistance of professional interpreters.

Participants can either read themselves or be read the consent form by a member of the research staff. After reviewing the consent form, all participants will be delivered the Assessment of Capacity, a teach-back process to ensure his/her understanding of the project, the purpose and procedures involved, and the voluntary nature of his/her participation. Those who have difficulty answering the items on the capacity questionnaire will have the study re-explained by research staff with a focus on aspects they did not understand. Those who demonstrate understanding of the study and voluntarily agree to participate will be asked to sign the Informed Consent Form.

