### Parent-Reported Study Assessments

In addition to the baseline assessments, all 60 participants (30 intervention and 30 control) will complete follow-up assessments at 3, 6, and 12 months following the completion of baseline assessments. Follow-up assessments can be completed in person at the research office, in the participant's home, or remotely by phone or videoconference.

Participants in the intervention arm only will also be invited to participate in an in-depth exit interview once their intervention period is complete in order to collect feedback on the intervention content and strategy and explore putative intervention mechanisms. If participants refuse to participate in the exit interview, but complete the survey assessments, they will still be compensated.

At any of the assessment timepoints, if participants refuse to complete select questions in the assessments, but answer most questions, they will still be compensated.

It is anticipated that in some cases, two primary caregivers will desire to be part of the intervention. Other adult family members involved in primary caregiving may also participate in any intervention sessions as long as the consenting primary caregiver is present for all sessions and is the only one completing all intervention assessments.

At baseline, participants will complete a Contact Information form that details their preferred mode of contact for completion of follow-up assessment (email, phone, mail). At each subsequent time point, RAs will refer to the contact information form and send reminders (via email, phone, or text message, based on preference) to the participant to complete their follow-up assessments every 4 days for at least 2 weeks (or until the assessment is complete). RAs will run weekly reports off REDCap to see which participants have not completed their assessments. If a participant has not completed their assessment after 2 weeks, the RA will call the participant to complete the assessment over the phone. At each of the follow-up timepoints (3, 6, and 12-months after baseline), RAs should stop reminder calls to participants 8 weeks after the participant was initially contacted to complete the assessment.

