### 12.3 Statistical Methods

Because this is a pilot study, it is not fully powered to detect differences between groups. Because of emerging consensus that group-to-group comparisons in a pilot study are invalid and misleading, estimating effect size is not one of our study objectives. However, our goal will be to obtain estimates of study parameters to inform power calculations for a subsequent study, including the following:

- Within-group standard deviation of each continuous primary and secondary outcome measure as well as each measure of target engagement; and
- Correlation over time of each outcome measured at baseline and follow-up.

Furthermore, our collection and analysis of process measures will be used to inform changes to the intervention throughout the pilot study in order to optimize its delivery for a future RCT.

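### Does the CBCL 1.5-5 need a written rule for children who pass its labelled age range during follow-up?

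*Combined protocol and SAP*

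**What the plan says.** Section 4.2.1 lists two primary clinical outcomes: the ADHD-RS-IV Preschool Version and "Child Psychiatric Symptoms (Child Behavior Checklist 1.5-5". Section 6.2 gives the age label again: "the CBCL for ages 1.5-5 and ADHD-RS-IV Preschool Version". The Schedule of Events names the same CBCL form in a single row. That row is marked at month 0, not at month 3, at month 6, and in one later column whose header is lost in the text available here. Month 12 is the natural reading of that column.

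On age, 3.2 equates three to five years with 36-71 months ("low-income children age 3-5 (36-71 months) with ADHD symptoms"), and 7.1 uses the same limits ("Legal guardian and primary caregiver of a child aged 36-71 months"). No age limit applies after entry. In section 9, all participants "will complete follow-up assessments at 3, 6, and 12 months following the completion of baseline assessments".

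Section 12.3 sets no group comparison. It asks for the within-group SD of each continuous outcome and for "Correlation over time of each outcome measured at baseline and follow-up", to inform the power calculation of a later trial. It names no score type for any outcome and makes no exclusion by age.

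**The concern.** A primary outcome is measured with a form labelled for children up to age five, in a sample that can enter at almost six and is followed for twelve months. Part of the sample must outgrow the label. The plan does not say whether the form is kept for those children, whether raw or normed scores are analysed, or whether their number will be reported.

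What would be at stake is the pilot's main quantitative product. If the form or the score changed between visits for some children, a baseline-to-follow-up correlation would not be clearly defined. If normed scores were used and did not cover the older children, the month-12 figures would rest on fewer children than a reader would suppose.

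The consent procedures appear to add a second route. After screening, "participants will have a period of 3 months to decide their participation and schedule a study visit", and only then "After the 3-month period, interested participants will be required to be re-screened as eligibility criteria may have changed". A child near the upper limit at screening might be past it by baseline.

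**Working it through.** **Inputs.** Entry at 36-71 completed months (7.1), which is 36 monthly cells. CBCL at months 0 and 6, and by inference month 12 (Schedule of Events, with section 9). Enrolment of 60, 30 per arm (4.1). Attrition of 25% (12.2). Reminders continue for up to 8 weeks after first contact (section 9). The label 1.5-5 is read as ending at 71 months, following 3.2. The documents give no limit in months for the form itself.

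**The plan's own figure.** The only arithmetic in 12.2 is 30 × (1 − 0.25) = 22.5 per group, which is above the 15 per group it cites. It holds. There is no alpha, power or effect size to reproduce.

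**Ages at follow-up.**
- Month 6: entry at 66-71 gives 66 + 6 = 72 to 71 + 6 = 77 months.
- Month 12: entry at 60-71 gives 60 + 12 = 72 to 71 + 12 = 83 months.

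**Share past 71 completed months, uniform entry ages (assumption).**
- Month 6: 6/36 = 16.7%; × 60 = 10; × 45 = 7.5 after attrition.
- Month 12: 12/36 = 33.3%; × 60 = 20; × 45 = 15 after attrition.
- If every assessment came 2 months late, at the end of the reminder window: 8/36 = 22.2% and 14/36 = 38.9%, about 13 and 23 of 60.

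**Range for other age mixes (assumption).** Let *p* be the share aged five at entry, spread evenly over that year. The share past the label is *p*/2 at month 6 and *p* at month 12. For *p* from 10% to 50% this gives 5-25% (3-15 of 60) and 10-50% (6-30 of 60). Even at *p* = 10%, the chance that at least one of 60 is past the label at month 6 is 1 − 0.95^60 = 95%.

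**Delay between screening and baseline.** If age were checked only at screening and every family took 3 months, the shares would be 3/36 = 8% at baseline, 9/36 = 25% at month 6 and 15/36 = 42% at month 12. These are not ceilings: adding the 2-month window gives 11/36 = 31% at month 6 and 17/36 = 47% at month 12. If age is re-checked at consent, the baseline share is zero. When the age criterion is checked is an eligibility matter, separate from how 12.3 analyses the CBCL.

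**What dropping the older children would do to 12.3.** At month 12, with uniform ages and 25% attrition, the pairs would fall from 60 × 0.75 = 45 to 45 × 2/3 = 30.
- Pooled within-group SD, 95% interval √(df/χ²), with df = *n* − 2. For df 43: √(43/62.99) = 0.826 and √(43/26.79) = 1.267, so −17%/+27%. For df 28: √(28/44.46) = 0.794 and √(28/15.31) = 1.352, so −21%/+35%.
- Correlation, assumed 0.6, by Fisher's z: tanh(0.693 ± 1.96/√(*n* − 3)). For *n* = 45: 0.37-0.76. For *n* = 30: 0.31-0.79.

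The loss of precision is modest, and 30 pairs is 15 per arm, the level 12.2 cites for group means. It would arise only if scores were set aside, and no section says that they are.

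**The case for a change.** The best case for a change is that the age mismatch comes from the protocol's own figures, that it is almost certain to affect some children, and that it touches a primary outcome. A sentence fixing the form and score type before analysis, with a count of the children concerned, would cost almost nothing and would rule out a choice made after seeing the data.

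The arithmetic stands, and so does the absence of a stated score type. The rest is weaker.

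- **The form is not really open.** One form is named in 4.2.1, 6.2, section 9 and the Schedule of Events, and no alternative for older children appears anywhere.
- **Keeping or dropping scores is not an even choice.** Section 12.3 takes each outcome without exclusion, and the section on removal of participants tries to keep even withdrawn families in follow-up. Setting scores aside has no support in the text.
- **A remedy would settle little.** The form and score would still be for the investigators to choose, and a count cannot show whether the form behaves differently at 72-83 months. If the full-sample SD and correlation stay as the planning figures, the contrast of 45 with 30 pairs has no consequence.
- **The silence on score type is general.** Section 12.3 gives none for any outcome, so this is a wish for more detail and not a fault specific to the CBCL.

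**Conclusion.** No change is needed. Some children will pass the form's labelled range: about 17% at month 6 and 33% at month 12 if entry ages are uniform, with 5-25% and 10-50% for the other age mixes tried, and somewhat more if questionnaires come in late. These shares rest on assumed age distributions, on reading the label as ending at 71 months, and on a month-12 CBCL visit inferred from a damaged table.

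The plan read plainly repeats the same form and uses every score. That keeps the measure constant between baseline and follow-up, which is what a correlation over time requires. Whether scores or norms fail past 71 months cannot be judged from these documents, and they do not show the planned SD or correlation to be wrong. In a pilot with no effect estimate and no group comparison, the score type and the number of older children are reporting details that the analysts can be expected to state with the results.

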## 6.3 Analysis of Risks in Relation to Benefits

The risk to participants in this study is quite minimal, as they include potential subjective discomfort through discussing social needs that are unmet, potential for subject burden, and potential breach in confidentiality. Conversely, the potential benefits to being involved in this study are substantial. Although Boston Medical Center Pediatrics and its affiliated pediatric practices generally have social needs assessment and care coordination available (control arm), PRE-CARE is designed to be a more comprehensive and tailored form of screening and referral for this population, and the research assessments will provide more detailed emotional and behavioral symptom information than is typically available in a primary care setting. Thus, participants have the opportunity to directly benefit from the study, besides the benefit to

society of testing a new intervention to improve ADHD symptoms in preschoolers, who are generally more difficult to treat than older children with ADHD.

## 7 Study Subject Selection

### 7.1 Subject Inclusion Criteria

In order to be eligible to participate in this study, an individual must meet all of the following criteria:

1. Legal guardian and primary caregiver of a child aged 36-71 months
2. Legal guardian or primary caregiver is age 16 years or older
3. Child receives pediatric care at Boston Medical Center or at one of the participating Boston HealthNet clinics
4. Able to understand informed consent procedures in English or Spanish
5. Participant has a child aged 36-71 months with an ADHD diagnosis, OR one elevated total or subscale score at the 80th percentile on the ADHD-Rating Scale-IV Preschool Version. 80th percentile cut-offs on the ADHD-Rating Scale-IV Preschool Version are as follows:
  - For male children, a total score  $\geq 25$  OR subscale score (inattention and/or hyperactivity)  $\geq 12$
  - For female children, a total score  $\geq 13$  OR subscale score (inattention and/or hyperactivity)  $\geq 6$  for female children

### 7.2 Subject Exclusion Criteria

There are no specific exclusion criteria for this study. We have chosen not to exclude families already receiving other ADHD services because they might also benefit from the intervention.

## 8 Study Intervention

Participants will receive the 1:1 PRE-CARE social needs navigation intervention with specific content and delivery strategy which was developed based on 1) quantitative analyses of the association between unmet social needs and ADHD symptoms in a large-scale nationally representative sample of children age 3-5, and 2) in-depth qualitative interviews with parents/guardians of preschoolers with inattention and/or hyperactivity symptoms to identify mechanisms by which unmet social needs exacerbate ADHD symptoms and functioning.

Based on an enhanced WE CARE model, the PRE-CARE intervention includes:

1. **Screening.** Parent-report screening for remediable, unmet social needs.
2. **Resource Packet.** Provision of packet of resource sheets ("Family Resource Booklet") detailing local community-based resources to address these needs, with needs that respond to family's requests highlighted.
3. **Resource Navigation.** Navigation to resources, care coordination, and parent support provided by a trained bachelors-level interventionist who is a member of the research study staff.

The planned duration of the intervention will be until:

1. All needs have been addressed,
2. Family requests termination of the program, OR
3. Three months have passed

***Intervention Part 1, Screening.*** First, parents will complete the PRE-CARE screener. The screener is designed as a parent-report, to be filled out either on paper or electronically using a link sent via text or email using Twilio and REDCap to our REDCap intervention database. If needed, the interventionist can read the questions out loud to the parent and record their answers. The social needs screening questions (which can be seen in full as an attachment to this IRB application) inquire about the following needs using the original WE CARE questions, due to their validity and effectiveness as shown in other studies: childcare, employment, housing, food, parent education, and utility bill payment ease. The PRE-CARE screener also assesses the following additional social needs categories: access to public benefits, paying taxes, school services/special education, parent mental health, parent physical health, child behavioral health, and extracurricular activities. The screener asks two questions about each need assessed. First, it asks whether there is a need or a risk (i.e., "Do you have trouble paying your heating/cooling, water or electricity bill?"). Next, if the answer is yes, there is a follow up question about whether the participant would like help with that particular item ("If yes, would you like help with this?"). Following administration of the PRE-CARE screener, the interventionist will review the participant's responses in order to tailor the referral/resource provision phase of the intervention.

***Intervention Part 2, Resource Packet.*** The interventionist will physically give (or send by email and/or regular mail if they are not meeting with the parent in person) a Family Resource Booklet. All families in the intervention arm will receive the full booklet, with written resources for all categories of needs assessed in the PRE-CARE screener. The Family Resource Booklet lists 3-5 community resources for each category of need, including a brief description of the services provided by the community agency, contact information, cost, location, and eligibility details. Interventionists will highlight in the resource booklet the areas that particularly address the needs indicated by families. Along with the resource booklet, the interventionist will provide participants with their own contact information. Resource guides will be updated regularly to ensure that they remain up to date and most helpful to participants.

***Intervention Part 3, Resource Navigation.*** Interventionists will discuss further with families the details of specific needs indicated during screening in order to best tailor assistance provided. Based on this conversation, the interventionist may offer more intensive support navigating to certain resources for families where it is needed. Interventionists will have a companion Navigation Resource Booklet that includes workflows and algorithms to assist with referral decisions for families. The level of interventionist involvement will be based on the family's particular needs, community resources available, and a shared decision-making process between the interventionist and family. For example, some participating parents may choose to

simply contact agencies listed in the Family Resource Booklet on their own, and not request any further support from the interventionist. Other families may want more assistance contacting and accessing community resources. In these cases, the interventionist may place referrals, coordinate services, or contact community agencies and providers on behalf of the family to inquire about resources.

As a default, the interventionist will offer follow-up meetings with the participating caregiver (either in-person, by phone, or via videoconference) every two weeks until three months have passed since the randomization date. The interventionist may end the intervention period later for the participant whose needs require longer than three months to resolve. The interventionist may also end the intervention period earlier than three months for the participant if all needs mentioned by the participant have been resolved. All forms of interventionist contacts (in-person appointments, emails, phone, and text message exchanges) and community resources placed on behalf of participating families will be documented in the participant's electronic medical record and logged by the interventionist in the study record. Interventionists will also log the length of time per contact. At each contact, interventionists will also inquire about resources received since last contact, and about whether additional help is needed for that need, or other (even new) needs. They will also ask for feedback about resources received and our process for helping families. Contacts will vary in time length (e.g., 5-10 minute calls vs. 1 hour long meetings) depending on the needs of each family.

